Appendix 13.1 Acute skin reaction

- Search in 'Skin and subcutaneous tissue disorders' SOC the following preferred term:
- Dermatitis (any Preferred Term that includes the word "dermatitis")
- Drug eruption
- Eczema
- Erythema multiforme
- Erythema nodosum
- Rash (any PT that includes the word "rash")
- Skin lesion
- Skin reaction
- Skin exfoliation
- Stevens-Johnson Syndrome
- Toxic epidermal necrolysis
- Toxic skin eruption
- Urticaria

Appendix 13.2 Involvement of at least 1 internal organ

Blood and lymphatic system disorders SOC	Cardiac disorders SOC:	Endocrine disorders SOC:
Agranulocytosis Aplastic anemia Aplasia pure red cell Autoimmune lymphoproliferative syndrome Autoimmune neutropenia Autoimmune pancytopenia Blood disorder Bone marrow disorder Bone marrow failure Bone marrow toxicity Coagulopathy Disseminated intravascular coagulation Disseminated intravascular coagulation in newborn Drug reaction with eosinophilia and systemic symptoms Eosinophilia Febrile neutropenia Granulocytopenia Haemolytic anemia Hemolysis Hypereosinophilic syndrome Leukemoid reaction Leukopenia Lymphocytosis Lymphopenia Hypersensitivity vasculitis Lymphadenitis Lymphadenopathy Lymphoma Monocytosis Mononucleosis Neutropenia Pancytopenia Platelet disorder Platelet toxicity Splenitis Splenomegaly Splenosis Thrombocytopenia	Autoimmune myocarditis Cardiomyopathy Endocarditis Eosinophilic myocarditis Myocarditis Pericarditis Pericardial effusion Pericardial disease Pleuropericarditis	Adrenalitis Autoimmune thyroiditis Thyroiditis

Eye disorders SOC	Gastrointestinal disorders SOC	Hepatobiliary disorders SOC
Eye allergy	Allergic colitis	Autoimmune hepatitis
Eye swelling	Colitis	Amylase increased
Iritis	Eosinophilic colitis	Blood trypsin increased
Iridocyclitis	Eosinophilic oesophagitis	Cholangitis
Optic neuritis	Gastritis	Cholecystitis
Retinitis	Gingival edema	Hepatic failure
Uveitis	Gingival swelling	Hepatic functional abnormal
Vitritis	Gingivitis	Hepatic encephalopathy
Scleritis	Glossitis	Hepatic infiltration eosinophilic
	Enteritis	Hepatitis
	Mouth ulceration	Hepatitis acute
	Mesenteritis	Hepatitis toxic
	Edema mouth	Hepatocellular injury
	Oropharyngeal swelling	Hepatomegaly
	Parotitis	Hepatosplenomegaly
	Pancreatitis	Hepatorenal failure
	Periodontitis	Hepatorenal syndrome
	Sialadenitis	Hepatotoxicity
	Stomatitis	Hyperbilirubinemia
	Swollen tongue	Hyperbilirubinemia neonatal
	Tongue oedema	Hyperlipidemia
	Vasculitis gastrointestinal	Jaundice
		Jaundice neonatal
		Liver disorder
		Lipase abnormal
		Lipase increased
		Edema due to hepatic disease
		Edematous pancreatitis
		Pancreatic enzymes increased
		Pancreatic hemorrhage
		Pancreatic necrosis
		Pancreatitis (any PT that includes the word "pancreatitis")
		Pancreatorenal syndrome
		Peripancreatic fluid collection
		Swollen tongue

General disorders and administration site conditions SOC:	Immune system disorders SOC (Part 1)	Immune system disorders SOC (Part 2)
Influenza like illness	Allergic bronchitis	Eyelid edema
Malaise	Allergic cough	Eosinophilic fasciitis
Multi-organ failure	Allergic cystitis	Face edema
Neonatal multi-organ failure	Allergic keratitis	Hypersensitivity
	Allergic oedema	Immune thrombocytopenic purpura
	Allergic sinusitis	Glomerulonephritis
	Alveolitis allergic	Laryngeal edema
	Anaphylactic reaction	Lip edema
	Anaphylactic shock	Lip swelling
	Anaphylactoid reaction	Myasthenia Gravis
	Anaphylactoid shock	Myositis
	Asthma	Nephrogenic systemic fibrosis
	Angioedema	Edema mouth
	Antiphospholipid syndrome	Panniculitis
	Autoimmune disorder	Pemphigus
	Autoimmune hepatitis	Pemphigoid
	Biliary cirrhosis primary	Periorbital edema
	Biliary cirrhosis	Pruritus allergic
	Bronchospasm	Polymyositis
	Circumoral edema	Reaction to drug excipients
	Cholangitis sclerosing	Sarcoidosis
	Dermatomyositis	Serum sickness
	Drug hypersensitivity	Systemic lupus erythematosus
	Drug reaction with eosinophilia and systemic symptoms	Systemic sclerosis
	Encephalitis	Type IV hypersensitivity reaction
	Encephalopathy allergic	Vitiligo

Investigations SOC: Hematologic	Investigations SOC: Immunologic	Investigations SOC: others
Any PT that reflects increased, decreased or abnormal MedDRA Hematology investigations (incl blood groups) HLGT Any PT that reflects increase or abnormal under MedDRA Hepatobiliary investigations HLGT	Any PT that reflects a positive or abnormal result under MedDRA Immunology and allergy investigations HLGT, and Investigations, imaging and histopathology procedures NEC, HLGT	Alanine aminotransferase Amylase Aspartate aminotransferase Bilirubin conjugated Blood amylase Blood bilirubin Blood bilirubin unconjugated Gamma-glutamyltransferase increased Lipase Liver function test Transaminases Biopsy liver abnormal Lung Biopsy lung abnormal Renal Blood creatinine increased Blood creatinine abnormal Blood urea increased Blood urea abnormal Creatinine renal clearance decreased Glomerular filtration rate decreased Blood urine Cells in urine Eosinophils urine Protein urine Red blood cells urine Urinary casts Urinary casts present Biopsy kidney abnormal Skin Biopsy skin abnormal

Musculoskeletal and connective tissue disorders SOC:	Neoplasms benign, malignant and unspecified (including cysts and polyps) SOC	Nervous system disorders SOC
Arthralgia Arthritis Arthroplasty Ankle arthroplasty Hip arthroplasty Joint arthroplasty Knee arthroplasty Shoulder arthroplasty Joint swelling Joint warmth Lupus-like syndrome Myopathy Myositis Polyarthritis Tendonitis Tenosynovitis Synovitis Any PT under the MedDRA Connective tissue disorders (excl congenital) HLGT.	Lymphoma (any PT that includes the word "lymphoma") Pseudolymphoma	Acoustic neuritis Arachnoiditis CNS inflammation CNS ventriculitis Spinal cord infection Encephalitis (all PTs under Encephalitis NEC, HLT) Encephalopathy Leukoencephalopathy Leukoencephalomyelitis Meningitis (all PTs under Meningitis NEC, HLT) Myelitis Neuritis cranial Neuropathy peripheral Polyneuropathy Reye's syndrome Toxic optic neuropathy Vasculitis cerebral

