#### **8.1.1 Dose Administration**

For all treatment sequences, IMP will be administered by the patient via a pump actuation of oromucosal spray. The IMP will be self-administered to the oral mucosa. Patients will receive IMP dosing training from site staff on Visit 2 (Day 1 predose). Patients will be advised to administer IMP at approximately the same time each day in a consistent manner in relation to food consumption. Morning and evening doses should be administered around the same time within 30 minutes after starting a snack or meal. Patients should divide doses greater than 1 spray/day into a morning dose and an evening dose. On the days of scheduled MAS assessments other than Visit 1 (i.e., Visits 2, 5, 6, and 9), patients will attend the trial site without having administered any IMP in the morning. On the days of MAS assessment, patients who are taking antispasticity therapy should take their regular morning dose at least 1 hour before the administration of IMP. Administration of the morning dose of IMP with a standardized snack containing at least 300 kcal (of which approximately 30 kcal is composed of fat) will occur at the trial site under the supervision of site staff.

Following the titration phase (see [Section 8.1.2](#)), IMP will be administered as 1 spray (100 µL per spray) with a target interval of approximately 1 minute, until the patient's specific optimized dose has been administered. Patients should be advised to direct each spray at a different site on the oromucosal surface, changing the application site for each spray of the IMP. If lesions are observed or persistent soreness is reported, the IMP administration must be interrupted until complete resolution occurs. Events of this nature are to be recorded according to the adverse event (AE) procedures (see [Section 12](#)).

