12.7.1 Adverse Events

Adverse events (AEs) will be coded using MedDRA 24.0 or higher according to the version in use at time of database lock. All safety analyses of AEs will be performed by actual treatment arm and reported using the Safety Analysis Set. An AE will be considered a TEAE if it first occurs or worsens in severity or seriousness after the first dose of IMP intake and before the last dose date + 15 days.

All AEs will be classified during the pre-treatment period, the 51-day safety on-treatment period or during the follow-up period as follows:

Events that occurred before first IMP intake without worsening or becoming serious after the first IMP dose are classified as **pre-treatment AEs**;

Events that occurred or worsens between first IMP dose and 14 days after IMP last dose are classified as on-treatment AE and are defined as **treatment-emergent AEs** (TEAEs);

- TEAE occurring during 21-day on-treatment safety Period 1 will be considered emergent to actual treatment received during Period 1 (as defined in [Section 10.1.1](#)).
- TEAE occurring during 21-day on-treatment safety Period 2 will be considered emergent to actual treatment received during Period 2 (as defined in [Section 10.1.1](#)).

Events occurring more than 15 days after last dose are classified as **follow-up AEs**.

Consequently, TEAEs will be summarized by treatment arm using the actual treatment received at each given period. Any adverse event occurring during the wash-out period will be linked to the actual treatment arm defined for Period 1, whereas any AEs occurring after last IMP dose will be linked to the actual arm defined at time of permanent study drug discontinuation.

The following events will not be identified as AEs in this study:

- Medical or surgical procedures (e.g., surgery, endoscopy, tooth extraction, etc.). The condition (the “triggering event”) that leads to the procedure are adverse events and will be reported as such.

- Pre-existing conditions present or detected prior to the first dose of study drug that do not worsen during the study.

Counting rules

For incidence reporting, if a patient reported more than one AE that was coded to the same preferred term/system organ class within a given treatment arm, the patient will be counted only once for that specific preferred term/system organ class by treatment arm and the rules defined below will be applied.

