Appendix 12 Category of Adverse Events of Special Interest

List number	Category of adverse events of special interest
01	Falls and injuries
02	Drug reaction with eosinophilia and systemic systems
03	Disorientation and confusion
04	Driving and road traffic accident
05	Abuse liability
06	Abnormal liver adverse events
07	Somnolence and sedation
08	Fatigue and lethargy
09	Suicidal ideation and behavior
10	Significant cardiovascular disease
11	Cognitive function
12	Depression and depressed mood
13	Psychiatric disorders
14	Seizures

Appendix 13 Modify registry of severe cutaneous adverse reaction criteria for Drug reaction with eosinophilia and systemic systems (DRESS)

Only patients meeting the criteria will be presented.

At least 3 of the following criteria should be present for hypersensitivity syndrome or DRESS:

- 1. Acute skin rash
- 2. Involvement of at least 1 internal organ
- 3. Enlarged lymph nodes of at least 2 sites
- 4. One of the following blood count abnormalities (limits provided by laboratory):
 - lymphocytes above or below the laboratory limits
 - eosinophils above the laboratory limits (in % or absolute count)
 - platelets below the laboratory limits
- 5. Fever above 38 degrees Celsius

The adverse events should occur within 30 days of each other (There should be temporal proximity for the onset of these AEs.). Some PTs may be mentioned in more than one SOC. (within 1 month of each other).

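### The DRESS organ list in SAP Appendix 13.2 has no renal or respiratory disorder terms and counts malaise and influenza like illness as organ involvement

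*SAP*

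**What the plan says.** SAP Appendix 11 names DRESS as an adverse event of special interest and defines its search solely by Appendix 13. The opening text of Appendix 13 lists five criteria: acute skin rash, internal organ involvement, enlarged lymph nodes at two or more sites, a blood count abnormality, and fever. The rule is "At least 3 of the following criteria should be present for hypersensitivity syndrome or DRESS", with the events within 30 days of each other. The output rule is "Only patients meeting the criteria will be presented".

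Criterion 2 is scored from the list under "Appendix 13.2 Involvement of at least 1 internal organ". Terms are arranged by system organ class (SOC), and the last heading is "Nervous system disorders SOC". Within the investigations class, one column groups findings by organ, for example "Lung Biopsy lung abnormal Renal Blood creatinine increased Blood creatinine abnormal Blood urea increased". The general disorders column contains influenza like illness, malaise and two multi-organ failure terms.

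Criterion 4 (Appendix 13.4) uses laboratory values against reference ranges and requires no change from baseline. The SAP addendum keeps treatment-emergent adverse events (TEAEs) and laboratory data as planned in the SAP. It does not name events of special interest or DRESS.

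**The concern.** The list does not match its own heading in two places. It treats kidney and lung as organs that count, because it gives them sub-headings under investigations, yet it has no column for diagnoses in either organ. It also accepts two constitutional terms that identify no organ.

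Because the output shows only patients who reach 3 of 5, a patient one criterion short does not appear in the DRESS display at all. DRESS is rare and serious, so one patient wrongly left out or wrongly shown changes how that display reads.

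**Working it through.** No sample size, power or alpha figure bears on this point, so there is no plan figure to reproduce. The check is a reading of the list and a scoring of the rule.

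**1. Coverage.** Appendix 13.2 has five tables of three columns, so 5 × 3 = 15 columns. The immune class takes two columns and investigations takes three, so the number of SOCs is 15 − 1 − 2 = 12: blood, cardiac, endocrine, eye, gastrointestinal, hepatobiliary, general, immune, investigations, musculoskeletal, neoplasms and nervous system. Renal and urinary: 0. Respiratory: 0.

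**2. Partial cover that does exist.**
- Kidney: 14 laboratory, urine and biopsy terms under investigations; glomerulonephritis in the immune column; hepatorenal and pancreatorenal terms in the hepatobiliary column.
- Lung: an abnormal lung biopsy term under investigations; allergic alveolitis, allergic bronchitis, asthma and bronchospasm in the immune column.

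**3. When criterion 2 decides.** Patterns with at least 3 of 5 criteria: C(5,3) + C(5,4) + C(5,5) = 10 + 5 + 1 = 16. Patterns with exactly three criteria, one of them organ involvement: C(4,2) = 6. In those 6 the content of the list settles whether the patient is shown.

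**4. Scored profiles.** The unlisted kidney and lung diagnoses are illustrative and do not come from the documents.

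| Profile | Rash | Organ | Nodes | Count | Fever | Score |
|---|---|---|---|---|---|---|
| Rash, pyrexia, tubulointerstitial nephritis | 1 | 0 | 0 | 0 | 1 | 2 |
| Rash, pyrexia, interstitial lung disease | 1 | 0 | 0 | 0 | 1 | 2 |
| Rash, pyrexia, acute kidney injury, creatinine increase reported as an AE | 1 | 1 | 0 | 0 | 1 | 3 |
| Rash, pyrexia, interstitial lung disease, eosinophils high | 1 | 0 | 0 | 1 | 1 | 3 |
| Dermatitis, malaise, lymphocytes out of range | 1 | 1 | 0 | 1 | 0 | 3 |
| Influenza like illness, pyrexia as a separate AE, lymphocytes out of range | 0 | 1 | 0 | 1 | 1 | 3 |

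Rows 1 and 2 are not presented. Rows 3 and 4 show how such a case is rescued. Rows 5 and 6 are presented with no organ named.

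**5. How likely the rescue is.** Protocol 12.6, item A, has the site replace signs or symptoms with the diagnosis once one is made. A site following this may record the unlisted diagnosis and no separate creatinine AE, which makes rescue through the investigations terms less likely, though not impossible. Scheduled haematology is at Screening and Day 21 of each period (SAP 12.7.3), which limits rescue through criterion 4.

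**6. Order of magnitude for false cases, on assumed rates only.** Assume independence, with 10% of patients (5–20%) having a constitutional or mouth term, rash 3% (2–5%), fever 3% (2–5%) and blood count out of range 25% (10–40%).
- P(at least two of rash, fever, count) = 0.03 × 0.03 × 0.75 + 2 × 0.03 × 0.97 × 0.25 + 0.03 × 0.03 × 0.25 = 0.01545.
- Over the planned 190 patients: 190 × 0.10 × 0.01545 = 0.29, range 0.04 to 1.5.

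This includes mouth terms, ignores the 30-day rule and uses a planned number that was not reached, all of which push it up. Flu-like illness and fever tend to occur together, which pushes it down. It shows only that the count is small.

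**The case against.** **The kidney and lung gap is partial.** A reader might infer that these organs are absent from the list and that such cases will be missed. The documents do not support that. Step 2 shows real cover, and any out-of-range lymphocyte, eosinophil or platelet value adds a criterion. What stands is that coded renal and respiratory diagnoses do not count by themselves.

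**The flu-like example may count one illness twice.** It needs pyrexia recorded as its own AE, and Protocol 12.6, item A, works against that too. Presentation without a rash comes from the 3-of-5 rule, not from the list. The malaise and dermatitis profile does not have this weakness.

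**Joint replacement.** The list includes "Arthroplasty Ankle arthroplasty Hip arthroplasty Joint arthroplasty Knee arthroplasty Shoulder arthroplasty", and a reader might infer false cases from operations. SAP 12.7.1 excludes "Medical or surgical procedures (e.g., surgery, endoscopy, tooth extraction, etc" from adverse events, so these terms should not fire. They are untidy rather than harmful.

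**Mouth and swelling terms.** Of the 22 gastrointestinal terms, 11 are oral, and the product is sprayed on the oral mucosa. A reader might infer that all of these are errors. However, Protocol 8.1.1 is conditional ("If lesions are observed or persistent soreness is reported, the IMP administration must be interrupted until complete resolution occurs") and does not predict lesions. Appendix 13 also covers hypersensitivity syndrome as well as DRESS, so oral, lip, eyelid, face and allergic terms may be a deliberate choice of sensitivity over specificity.

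**A lost table.** The headings run roughly alphabetically and stop just before renal and respiratory would come. The contents list puts 13.2 at page 98 and 13.3 at page 103, and five pages fit five tables, so loss in text extraction is unlikely. It is not excluded, and the source file would settle it.

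**Limited consequence.** Every underlying event still appears in the TEAE tables by SOC and preferred term, in the serious event tables where relevant, and in the listings. No hypothesis test is involved.

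**Conclusion.** The point holds in limited form. Appendix 13.2 omits renal and respiratory disorder terms although its own sub-headings show that those organs are meant to count, and it accepts two terms that name no organ. For a patient at exactly two other criteria, either defect changes whether the patient is presented.

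Severity is minor. Only one descriptive category of special interest is affected, and efficacy is untouched. The number of patients affected cannot be derived from the documents: they give no rates for rash, fever, blood counts or the listed terms, and enrolment stopped before the planned number. An expected count of false cases would therefore be assumption, not finding.

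The conclusion rests on two assumptions: that the extracted list is complete, and that the DRESS output survives the abbreviated reporting. The second is inferred from the addendum keeping TEAEs as planned.

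**What to change.** Edit Appendix 13.2 before unblinding:

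- Add columns for renal and urinary disorders (acute kidney injury, renal failure and nephritis terms) and for respiratory, thoracic and mediastinal disorders (pneumonitis and interstitial lung disease terms).
- Remove malaise and influenza like illness.
- Remove the six arthroplasty terms, as tidying only.
- Keep the mouth terms, but flag in the output any case whose only organ term is oral, because of where the spray is applied.
- Leave the lip, eyelid, face and allergic terms to clinical review.

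The cost is a change to a search list and one flag in the output. The downside is slightly lower sensitivity for cases whose only non-skin sign is constitutional.

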Appendix 13.3 Enlarged lymph nodes of at least 2 sites

Search for PT including the word “Lymphadenopathy” alone or as part of another PT

Such as some examples are given below:

- Lymphadenopathy Mediastinal
- Paratracheal Generalized
- Retroperitoneal
- Vaccination site

Search for other PT that could reflect lymphadenopathy

- Benign lymph node neoplasm
- Lymph node palpable
- Lymph node scan abnormal

Appendix 13.4 One of the following blood count abnormalities

The search will use laboratory blood sample values along with their corresponding reference ranges

- Lymphocytes above or below lab limits
- Eosinophils above the lab limits
- Platelets below lab limits

Appendix 13.5 Fever above 38 degrees Celsius

The following selection will be performed based on AE

- Hyperthermia
- Hyperpyrexia
- Pyrexia
- Febrile bone marrow aplasia (and all PTs that include the word “febrile”)
- Body temperature increased
- Body temperature abnormal

Appendix 14 Overview of primary, secondary and exploratory efficacy objectives

Objective Clinical Category	Statistical Category	Estimand/Variable

Primary Objective: To evaluate the effect of multiple doses of nabiximols compared with placebo on a clinical measure of velocity-dependent muscle tone in the lower limbs (Lower Limb Muscle Tone-6; LLMT-6) in patients with multiple sclerosis (MS).
		
LLMT-6	P1, Primary	
Variable: Change from period baseline in LLMT-6 at Day 21 Population: FAS Regardless permanent treatment discontinuation Regardless premature study discontinuation Regardless major IPD Accounting for COVID-19 impact PLS: Mean difference between nabiximols and placebo Analysis: LSMD from CFB linear mixed-effect model for crossover data adjusted on period baseline LLMT-6 with placebo-based MI under MNAR assumption.

	P1, SA1 (Sensitivity)	
Variable: Change from period baseline in LLMT-6 at Day 21 Population: FAS Regardless permanent treatment discontinuation Regardless premature study discontinuation Regardless major IPD Accounting for COVID-19 impact PLS: Mean difference between nabiximols and placebo Analysis: LSMD from CFB linear mixed-effect model for crossover data adjusted on period baseline LLMT-6 with MI under MNAR assumption. Tipping point analysis

	P1, SUP1 (Supplementary , Subgroup)	Subgroup analyses based on same estimand as primary endpoint
	P1, SUP2 (response analyses)	
Variable: proportion of patients with LLMT-6 score reduction criterion cut-offs defined by different percentages of $\geq 20\%$, $\geq 30\%$, $\geq 40\%$, $\geq 50\%$ from period baseline in LLMT-6 at Day 21 Population: FAS IES: Regardless permanent treatment discontinuation Regardless premature study discontinuation Regardless major IPD Regardless COVID-19 impact PLS: Odd ratio in Nabiximols versus placebo Analysis: OR from logistic regression model for crossover data adjusted on period baseline LLMT-6. Single imputation: Missing Day 21 values are imputed a failure.

	P1, SUP 3 (Repeated measure analysis)	Variable: Change from period baseline in LLMT-6 at Day 21 Population: FAS IES: Regardless permanent treatment discontinuation Regardless premature study discontinuation Regardless major IPD Regardless deviation from time window at D1H3 Accounting for COVID-19 impact PLS: Mean difference between nabiximols and placebo Analysis: LSMD from CFB linear mixed-effect model with repeated measure for crossover data adjusted on period baseline LLMT-6 with placebo-based MI under MNAR assumption.
	P1, SUP4 (Supplementary without missing individual muscle group MAS score)	Variable: Change from period baseline in LLMT-6 at Day 21 Population: Study completer analysis set IES: Regardless permanent treatment discontinuation Without premature study discontinuation Regardless major IPD Accounting for COVID-19 impact Excluding LLMT-6 score derived with missing individual muscle group MAS score PLS: Mean difference between nabiximols and placebo Analysis: LSMD from CFB linear mixed-effect model for crossover data adjusted on period baseline LLMT-6 with placebo-based MI under MNAR assumption.
	P1, SUP5 (Supplementary without premature study discontinuation)	Variable: Change from period baseline in LLMT-6 at Day 21 Population: Study completer analysis set IES: Regardless permanent treatment discontinuation Without premature study discontinuation Regardless major IPD Accounting for COVID-19 impact PLS: Mean difference between nabiximols and placebo Analysis: LSMD from CFB linear mixed-effect model for crossover data adjusted on period baseline LLMT-6 with placebo-based MI under MNAR assumption.
	P1, SUP6 (Supplementary on-treatment assessment)	Variable: Change from period baseline in LLMT-6 at Day 21 Population: FAS IES: Prior permanent treatment discontinuation Regardless premature study discontinuation Without major IPD Accounting for COVID-19 impact PLS: Mean difference between nabiximols and placebo Analysis: LSMD from CFB linear mixed-effect model for crossover data adjusted on period baseline LLMT-6 with placebo-based MI under MNAR assumption.

	P1, SUP7 (Supplementary without major IPD impact)	Variable: Change from period baseline in LLMT-6 at Day 21 Population: PP analysis set IES: Regardless permanent treatment discontinuation Prior to major IPD Accounting for COVID-19 impact PLS: Mean difference between nabiximols and placebo Analysis: LSMD from CFB linear mixed-effect model for crossover data adjusted on period baseline LLMT-6 with placebo-based MI under MNAR assumption.
	P1, SUP8 (Supplementary without major IPD impact and without deviation from time window)	Variable: Change from period baseline in LLMT-6 at Day 21 Population: PP analysis set IES: Prior permanent treatment discontinuation Regardless premature study discontinuation Without major IPD Without deviation from time window at D1H3 Accounting for COVID-19 impact PLS: Mean difference between nabiximols and placebo Analysis: LSMD from CFB linear mixed-effect model with repeated measure for crossover data adjusted on period baseline LLMT-6 with placebo-based MI under MNAR assumption.
	P1, SUP9 (Supplementary without COVID-19 impact)	Variable: Change from period baseline in LLMT-6 at Day 21 Population: FAS IES: Regardless permanent treatment discontinuation Regardless premature study discontinuation Regardless major IPD Without COVID-19 impact PLS: Mean difference between nabiximols and placebo Analysis: LSMD from CFB linear mixed-effect model for crossover data adjusted on period baseline LLMT-6 with placebo-based MI under MNAR assumption.
Secondary objective (efficacy): To evaluate the effect of multiple doses of nabiximols compared with placebo on a clinical measure of velocity-dependent muscle tone in the lower limbs (Lower Limb Muscle Tone-4; LLMT-4) in patients with MS. .		
LLMT-4	S1, Primary	Variable: Change from period baseline in LLMT-4 at Day 21 Population: FAS IES: Regardless permanent treatment discontinuation Regardless premature study discontinuation Regardless major IPD Accounting for COVID-19 impact PLS: Mean difference between nabiximols and placebo Analysis: LSMD from CFB linear mixed-effect model for crossover data adjusted on period baseline LLMT-4 with placebo-based MI under MNAR assumption.

	S1, SA1 (Sensitivity)	Variable: Change from period baseline in LLMT-4 at Day 21 Population: FAS Regardless permanent treatment discontinuation Regardless premature study discontinuation Regardless major IPD Accounting for COVID-19 impact PLS: Mean difference between nabiximols and placebo Analysis: LSMD from CFB linear mixed-effect model for crossover data adjusted on period baseline LLMT-4 with MI under MNAR assumption. Tipping point analysis
	S1, SUP1 (Repeated measure analysis)	Variable: Change from period baseline in LLMT-4 at Day 21 Population: FAS IES: Regardless permanent treatment discontinuation Regardless premature study discontinuation Regardless major IPD Regardless deviation from time window at D1H3 Accounting for COVID-19 impact PLS: Mean difference between nabiximols and placebo Analysis: LSMD from CFB linear mixed-effect model with repeated measure for crossover data adjusted on period baseline LLMT-4 with placebo-based MI under MNAR assumption.
	S1, SUP2 (Supplementary without missing individual muscle group MAS score)	Variable: Change from period baseline in LLMT-4 at Day 21 Population: Study completer analysis set IES: Regardless permanent treatment discontinuation Without premature study discontinuation Regardless major IPD Accounting for COVID-19 impact Excluding LLMT-4 score derived with missing individual muscle group MAS score PLS: Mean difference between nabiximols and placebo Analysis: LSMD from CFB linear mixed-effect model for crossover data adjusted on period baseline LLMT-4 with placebo-based MI under MNAR assumption.
	S1, SUP3 (Supplementary without premature study discontinuation)	Variable: Change from period baseline in LLMT-4 at Day 21 Population: Study completer analysis set IES: Regardless permanent treatment discontinuation Without premature study discontinuation Regardless major IPD Accounting for COVID-19 impact PLS: Mean difference between nabiximols and placebo Analysis: LSMD from CFB linear mixed-effect model for crossover data adjusted on period baseline LLMT-4 with placebo-based MI under MNAR assumption.

	S1, SUP4 (Supplementary on-treatment assessment)	Variable: Change from period baseline in LLMT-4 at Day 21 Population: FAS IES: Prior permanent treatment discontinuation Regardless premature study discontinuation Without major IPD Accounting for COVID-19 impact PLS: Mean difference between nabiximols and placebo Analysis: LSMD from CFB linear mixed-effect model for crossover data adjusted on period baseline LLMT-4 with placebo-based MI under MNAR assumption.
	S1, SUP5 (Supplementary without major IPD impact)	Variable: Change from period baseline in LLMT-4 at Day 21 Population: PP analysis set IES: Regardless permanent treatment discontinuation Regardless premature study discontinuation Without major IPD Accounting for COVID-19 impact PLS: Mean difference between nabiximols and placebo Analysis: LSMD from CFB linear mixed-effect model for crossover data adjusted on period baseline LLMT-4 with placebo-based MI under MNAR assumption.
	S1, SUP6 (Supplementary without COVID-19 impact)	Variable: Change from period baseline in LLMT-4 at Day 21 Population: FAS IES: Regardless permanent treatment discontinuation Regardless premature study discontinuation Regardless major IPD Without COVID-19 impact PLS: Mean difference between nabiximols and placebo Analysis: LSMD from CFB linear mixed-effect model for crossover data adjusted on period baseline LLMT-4 with placebo-based MI under MNAR assumption.
Exploratory objective: To evaluate the effect of multiple doses of nabiximols compared with placebo on a clinical measure of velocity-dependent muscle tone in the lower limbs (Lower Limb Muscle Tone-10; LLMT-10) in patients with multiple sclerosis		
LLMT-10	E1, Primary	Variable: Change from period baseline in LLMT-10 at Day 21 Population: FAS IES: Regardless permanent treatment discontinuation Regardless premature study discontinuation Regardless major IPD Accounting for COVID-19 impact PLS: Mean difference between nabiximols and placebo Analysis: LSMD from CFB linear mixed-effect model for crossover data adjusted on period baseline LLMT-10 with placebo-based MI under MNAR assumption.
	E1, SUP1	Variable: Change from period baseline in LLMT-10 at Day 21

	Repeated measure analysis)	Population: FAS IES: Regardless permanent treatment discontinuation Regardless premature study discontinuation Regardless major IPD Regardless deviation from time window at D1H3 Accounting for COVID-19 impact PLS: Mean difference between nabiximols and placebo Analysis: LSMD from CFB linear mixed-effect model with repeated measure for crossover data adjusted on period baseline LLMT-10 with placebo-based MI under MNAR assumption
	E1, SUP2 (Supplementary without missing individual muscle group MAS score	Variable: Change from period baseline in LLMT-10 at Day 21 Population: Study completer analysis set IES: Regardless permanent treatment discontinuation Without premature study discontinuation Regardless major IPD Accounting for COVID-19 impact Excluding LLMT-10 score derived with missing individual muscle group MAS score PLS: Mean difference between nabiximols and placebo Analysis: LSMD from CFB linear mixed-effect model for crossover data adjusted on period baseline LLMT-10 with placebo-based MI under MNAR assumption.
	E1, SUP3 (Supplementary without premature study discontinuation	Variable: Change from period baseline in LLMT-10 at Day 21 Population: Study completer analysis set IES: Regardless permanent treatment discontinuation Without premature study discontinuation Regardless major IPD Accounting for COVID-19 impact PLS: Mean difference between nabiximols and placebo Analysis: LSMD from CFB linear mixed-effect model for crossover data adjusted on period baseline LLMT-10 with placebo-based MI under MNAR assumption.
	E1, SUP4 (Supplementary on-treatment assessment)	Variable: Change from period baseline in LLMT-10 at Day 21 Population: FAS IES: Prior permanent treatment discontinuation Regardless premature study discontinuation Without major IPD Accounting for COVID-19 impact PLS: Mean difference between nabiximols and placebo Analysis: LSMD from CFB linear mixed-effect model for crossover data adjusted on period baseline LLMT-10 with placebo-based MI under MNAR assumption.
	E1, SUP5 (Supplementary	Variable: Change from period baseline in LLMT-10 at Day 21 Population: PP analysis set

	without major IPD impact)	
IES:
 
Regardless permanent treatment discontinuation
 
Regardless premature study discontinuation
 
Without major IPD
 
Accounting for COVID-19 impact
 
PLS: Mean difference between nabiximols and placebo
 
Analysis: LSMD from CFB linear mixed-effect model for crossover data adjusted on period baseline LLMT-10 with placebo-based MI under MNAR assumption.

	E1, SUP6 (Supplementary without COVID-19 impact)	
Variable: Change from period baseline in LLMT-10 at Day 21
 
Population: FAS
 
IES:
 
Regardless permanent treatment discontinuation
 
Regardless premature study discontinuation
 
Regardless major IPD
 
Without COVID-19 impact
 
PLS: Mean difference between nabiximols and placebo
 
Analysis: LSMD from CFB linear mixed-effect model for crossover data adjusted on period baseline LLMT-10 with placebo-based MI under MNAR assumption.

Exploratory Objective: To evaluate the effect of nabiximols after administration of multiple doses on walking using the Timed 25-Foot Walk (T25FW) test.
		
T25FW	E2, Primary	
Variable: Change from period baseline in average 25-foot walk time at Day 21
 
Population: FAS
 
IES:
 
Regardless permanent treatment discontinuation
 
Regardless premature study discontinuation
 
Regardless major IPD
 
Regardless COVID-19 impact
 
PLS: Mean difference between nabiximols and placebo
 
Analysis: LSMD from CFB linear mixed-effect model for crossover data adjusted on period baseline average T25FW. Single imputation at trial level: missing trial time are imputed to 180 seconds under MAR assumption

	E2, S1 (without missing trial time imputation)	Variable: Change from period baseline in average 25-foot walk time at Day 21 Population: FAS IES: Regardless permanent treatment discontinuation Regardless premature study discontinuation Regardless major IPD Regardless COVID-19 impact PLS: Mean difference between nabiximols and placebo Analysis: LSMD from CFB linear mixed-effect model for crossover data adjusted on period baseline average T25FW. No imputation under MAR assumption
	E2, SUP1 (response analysis)	Variable: proportion of patients with a 20% decrease from period baseline in average T25FW at Day 21 Population: FAS IES: Regardless permanent treatment discontinuation Regardless premature study discontinuation Regardless major IPD Regardless COVID-19 impact PLS: Odd ratio in Nabiximols versus placebo Analysis: OR from logistic regression model for crossover data adjusted on period baseline average T25FW. Single imputation: Missing Day 21 values are imputed a failure.
	E2, SUP2 (Supplementary without major IPD impact)	Variable: Change from period baseline in average 25-foot walk time at Day 21 Population: PP analysis set IES: Regardless permanent treatment discontinuation Regardless premature study discontinuation Without major IPD Regardless COVID-19 impact PLS: Mean difference between nabiximols and placebo Analysis: LSMD from CFB linear mixed-effect model for crossover data adjusted on period baseline average T25FW. No imputation under MAR assumption
	E2, SUP3 (Supplementary without COVID-19 impact)	Variable: Change from period baseline in average 25-foot walk time at Day 21 Population: FAS IES: Regardless permanent treatment discontinuation Regardless premature study discontinuation Regardless major IPD Without COVID-19 impact. PLS: Mean difference between nabiximols and placebo Analysis: LSMD from CFB linear mixed-effect model for crossover data adjusted on period baseline average T25FW. No imputation under MAR assumption

Exploratory Objectives: To evaluate the effect of nabiximols after administration of multiple doses on the following patient-reported outcomes: the 11-point Numerical Rating Scale (NRS) spasticity score, Daily spasm count as well as the MS Spasticity Scale (MSSS-88) total and subdomain scores.

11-point NRS-spasticity score	E3, Primary	Variable: 7-day average NSR spasticity score at Day 21 Population: FAS IES: Regardless permanent treatment discontinuation Regardless premature study discontinuation Regardless major IPD Regardless COVID-19 impact PLS: Mean difference between nabiximols and placebo Analysis: LSMD from observed value linear mixed-effect model for crossover data. No imputation under MAR assumption
